Pilot Study of Motivational Interviewing for Loved Ones (MILO)

ClinicalTrials.gov number: NCT04010747

Protocol Version Number: 1

Protocol Version Date: 3 March 2021

NCT04010747

Funding Mechanism: NIMH K23 MH118373

Principal Investigator: [name]

[contact] (cell)

E-mail: [contact]

Statistical Analysis Plan pages 15-17

CONFIDENTIAL

This document is confidential and the property of Boston Medical Center / Boston University. No part of it may be transmitted, reproduced, published, or used by other persons without prior written authorization from the study sponsor.

TABLE OF CONTENTS

1	List of Abbreviations	3
2	Protocol Summary.....	3
3	Background/Rationale & Purpose	3
3.1	Background Information	3
3.2	Rationale and Purpose	4
4	Objectives.....	4
4.1	Study Objectives	4
4.2	Study Outcome Measures.....	5
4.2.1	Primary Outcome Measures.....	5
4.2.2	Secondary Outcome Measures	5
5	Study Design.....	6
6	Potential Risks and Benefits.....	7
6.1	Risks	7
6.2	Potential Benefits.....	9
6.3	Analysis of Risks in Relation to Benefits.....	9
7	Study Subject Selection	9
7.1	Subject Inclusion Criteria.....	10
7.2	Subject Exclusion Criteria	10
8	Study Intervention	10
9	Study Procedures.....	11
10	Assessment of Safety and Data Safety Monitoring Plan (DSMP).....	12
10.1	Definitions	13
10.2	Safety Review	13
10.3	Reporting Plans	14
10.4	Stopping Rules.....	14
11	Data Handling and Record Keeping.....	14
11.1	Confidentiality	14
11.2	Source Documents.....	15
11.3	Case Report Forms	15
11.4	Study Records Retention	15
12	Statistical Plan	15
12.1	Study Hypotheses	16
12.2	Sample Size Determination	16
12.3	Statistical Methods	16
13	Ethics/Protection of Human Subjects.....	17
14	Literature References	17

1 List of Abbreviations

Abbreviation	Abbreviation definition
MILO	Motivational Interviewing for Loved Ones
IP	Individual with Psychosis
PCSO	Parents and Concerned Significant Others

2 Protocol Summary

Title:	Pilot Study of Motivational Interviewing for Loved Ones (MILO)
Population:	Caregivers (age 18 or older) of individuals ages 15-35 experiencing early course psychotic disorders; N = 100
Intervention:	Motivational Interviewing for Loved Ones, "MILO" MILO consists of four 60-minute sessions of communication skills training delivered by a trained provider in person or via secure telehealth
Objectives:	Evaluate the effectiveness of MILO for (1) facilitating the engagement of IP with evidence-based treatments and (2) reducing distress among PCSO
Design/Methodology:	Participants will be randomly assigned to either receive MILO (50%) or the waitlist condition (50%) as a partial cross-over design.
Total Study Duration:	3/1/21-7/31/23
Subject Participation Duration:	Four to six months, depending on whether participant is assigned to immediate intervention vs. waitlist condition as well as the pace

3 Background/Rationale & Purpose

3.1 Background Information

First Episode Psychosis (FEP) often represents a time of crisis for young people and their families. Since peak onset occurs during late adolescence and early adulthood, the onset of serious mental health challenges can disrupt plans for education, relationships, and other milestones of independence. Although some psychoses are brief and self-limiting, more often these symptoms portend a potentially chronic and disabling psychiatric disorder such as schizophrenia. FEP can also be acutely dangerous: youth with FEP are far more likely to die in the year following their diagnosis relative to the general population of 16-30-year old's in the United States. Approximately 100,000 youth in the United States experience FEP every year. Young people identified by providers as experiencing FEP often slip through the cracks before they reach appropriate treatment. A review of privately insured adolescents and young adults in the US showed that 62% of young people in the US with FEP filled no outpatient prescriptions, and 41% received no outpatient psychotherapy, in the year following their index diagnosis. Among those who do have an initial encounter with specialized FEP outpatient care, high

attrition is a common problem, with 30% of individuals initially enrolled in first episode programs dropping out prior to completing treatment.

Many individuals experiencing psychosis are reluctant to seek mental health treatment due to lack of insight and fear of psychiatric interventions. Young adults may be torn between distress and dissatisfaction relating to their symptoms and functioning, and mistrust of mental health providers and irritation with their parents' concern. Motivational Interviewing (MI) techniques are designed to elicit this ambivalence through nonjudgmental listening, so that discrepancies between current behaviors and ideal outcomes can be explored. Clinician-delivered MI has been identified as effective for enhancing adherence once individuals with psychosis are involved in care, and MI may also be useful for engaging those who are not yet interested in treatment. Several studies have found positive results in training and deploying non-professionals to use MI to influence others' health behaviors. MI training for parents and concerned significant others (PCSO) is a promising venue through which PCSO can specifically influence their loved one's decision to seek care and adhere to treatment plans.

The PI ([name]) has developed a brief 4-5 session training course for caregivers called "motivational interviewing for loved ones" (MILO). Each training session lasts 45-60 minutes and consists of teaching the participant an MI based communication skill, reviewing previously discussed skills, or offering referral information for treatment for their IP. The training can be done in-person or virtually. In a feasibility focused pilot, the intervention was found to be highly valued by participants, with 94% of consented participants completing at least three sessions. This application represents the continuation of a pilot efficacy trial that was initiated at Beth Israel Deaconess Medical Center and which the PI would like to continue at Boston Medical Center.

This study will be conducted in compliance with the protocol, applicable regulatory requirements, and BMC/BU Medical Campus Human Research Protection policies and procedures.

3.2 Rationale and Purpose

MILO aims to address the critical problem of delayed treatment and under-treatment in early course psychosis by offering a motivational interviewing (MI) based skills intervention for parents or other concerned significant others (PCSO) of individuals with psychosis (IP) who refuse treatment. This intervention will offer psychoeducation and concrete skills for communicating with the IP about the potential benefits of seeking care. The primary aim of the intervention is to increase the likelihood of IP engaging with evidence-based treatment. Secondary outcomes include reductions in PCSO distress and increases in PCSO well-being.

4 Objectives

4.1 Study Objectives

The initial aim of this pilot study is to evaluate feasibility of the intervention. The secondary aims are to evaluate the effectiveness of MILO for (a) facilitating the engagement of IP with evidence-based treatments and (b) reducing distress among PCSO. We hypothesize that the intervention

will be superior to control condition for both enhancing IP engagement with mental health services and reducing PCSO distress.

4.2 Study Outcome Measures

4.2.1 Primary Outcome Measures

Feasibility will be analyzed using the following descriptive metrics: # participants screened; # Eligible; # Enrolled; # not enrolled and corresponding reasoning; # Meeting DSM-5 Adjustment Disorder criteria; Percentage of study sessions completed; study Satisfaction; % assessments completed; Duration of assessments. A demographics questionnaire, a clinician-administered assessment containing information relevant to the DSM-5 diagnosis of adjustment disorder, and the Client Satisfaction Questionnaire will be used.

4.2.2 Secondary Outcome Measures

Measurement of secondary outcomes will occur using the instruments in the table below.

Measure	Study Objective	Time Point
Absolute Worth and Autonomy Scale	Aim 2b: Reducing distress among PCSO	Baseline, Waitlist Condition, Post Intervention, 8 Week FU, 12 Week FU
Perceived Stress Scale	Aim 2b: Reducing distress among PCSO	Baseline, Waitlist Condition, Post Intervention, 8 Week FU, 12 Week FU
Conflict Behavior Questionnaire	Aim 2b: Reducing distress among PCSO	Baseline, Waitlist Condition, Post Intervention, 8 Week FU, 12 Week FU
SCORE-15 Index of Family Functioning	Aim 2b: Reducing distress among PCSO	Baseline, Waitlist Condition, Post Intervention, 8 Week FU, 12 Week FU
Parenting Self Agency	Aim 2b: Reducing distress among PCSO	Baseline, Waitlist Condition, Post Intervention, 8 Week FU, 12 Week FU
Family Questionnaire	Aim 2b: Reducing distress among PCSO	Baseline, Waitlist Condition, Post Intervention, 8 Week FU, 12 Week FU
Motivational Interviewing Skills Questions	Aim 2a: Feasibility	Baseline, Post- Intervention
Mental Health Service Use History	Aim 2a: Facilitating engagement of IP in treatment	Baseline
Past Month Service Use History	Aim 2a: Facilitating engagement of IP in treatment	Baseline, Waitlist Condition, Post Intervention, 8 Week FU, 12 Week FU
Change Questionnaire	Aim 2b: Reducing distress among PCSO	Post Intervention, 12 Week FU

10 Minute Audio Recorded Role Play	Aim 2a: Feasibility	Baseline, Waitlist Condition, Post Intervention
------------------------------------	---------------------	---

5 Study Design

[figure not shown]
The study population is parents and concerned significant others (PCSO) of individuals experiencing psychosis (IP) who are not currently engaged with treatment. The IP has to have a recent onset of psychosis within the past 5 years. MILO is a structured brief intervention that seeks to accomplish two aims. The primary aim is to facilitate the engagement of IP with evidence-based treatments. The secondary aim is to reduce the distress and increase the wellbeing of PCSO. The intervention will be trialed for feasibility and then tested against a small waitlist condition control arm. Participants will be randomly assigned to either receive MILO (50%) or the waitlist condition (50%) in a cross over design.

The study is designed to minimize participant burden. Concerns about the ethics of randomization are allayed by the fact MILO is untested (effectiveness is not proven), and that the control condition represents treatment as usual. Thus the risk benefit ratio, even for those assigned to “treatment as usual/waitlist”, is favorable given that typically no particular assistance is offered in the community for parents/significant others attempting to connect their loved one with care. Phase 1 of the study was completed at its initial site at Beth Israel Deaconess Medical Center. Phase 2 was also started at the previous sight and will be completed at Boston Medical Center.

We will be collecting data through REDCap surveys administered via email link to the participants. Those assigned to the MILO treatment condition will be assessed at 4 time points (study entry, post intervention, 8 week follow up, 12 week follow up). Those in the waitlist condition will be assessed at 5 time points (study entry, end of waitlist, post intervention, 8 week follow up, 12 week follow up). Please see the following measures:

- Participants Contact Information
- Demographics questionnaire
- SCID-5 Adjustment disorder module
- Absolute Worth and Autonomy Scale
- Perceived Stress Scale
- Conflict Behavior Questionnaire
- SCORE-15 Index of Family Functioning
- Parenting Self-Agency
- Family Questionnaire
- Motivational Interviewing Skills Questions
- Mental Health Service Use History & Past month Service Use History Forms
- Modified Client Satisfaction Questionnaire
- Change Questionnaire

- 10-minute audio-recorded standardized patient role play (at study entry and post-intervention and waitlist time points only; role-plays will be scored using the Motivational Interviewing for Loved Ones Skills Assessment.

6 Potential Risks and Benefits

6.1 Risks

Potential risks to PCSO participating in MILO include: 1) There is a potential risk that confidential health information collected during the course of the study may be disclosed to others. 2) Participating PCSO may at times feel inconvenienced by the time required to complete the sessions and/or research assessments. 3) Participants may experience frustration or anxiety in learning to use the motivational interviewing communication skills. They may experience sadness or discomfort when discussing personal problems or in interacting with a family member. Discussing or experiencing the IP's psychiatric problems may be upsetting to the family. 4) There is a potential risk that participants will be subjected to stigma or undue anxiety from identification with the study. 5) The individuals with psychosis will be discussed in detail during study sessions. These individuals might find it distressing to know that their circumstances are the topic of their loved ones' research participation.

The PI and study staff will take the following steps to protect against risks:

- 1) Confidentiality will be maintained by assigning each participant a study number, and coding all data collected with that number. Identifying information and study data will be stored separately on secure BMC servers. To protect the confidentiality of the IP being discussed, his/her name will not be written down anywhere. All computer databases will be password protected, and hard copies of all data and records will be stored in locked filing cabinets. All study personnel will be certified to conduct research with human subjects and will be aware of the importance of maintaining strict confidentiality. Audio recordings of participants will be saved in digital files on a secure BMC server. Audio files will be destroyed at the conclusion of the study unless explicit consent to use audio files (e.g. for training purposes) is obtained from participants.
- 2) The assessment battery has been designed to minimize participant burden.
- 3) The study PI is a very experienced clinician and will provide ongoing supervision to each individual working on the protocol to ensure that they are equipped to provide appropriate support when necessary and to recognize signs of distress and discomfort. It is not expected that participants will feel any more sadness or discomfort talking about personal problems or interacting with a family member than they would at home or if they took part in psychotherapy in the community. If participants or family members experience frustration or distress, the PI will offer participants emotional support and validation. She will also offer strategies for managing the situation and accompanying emotional responses. Participants will also be informed that they can receive and follow-up on outside referrals for counseling outside of the study at any time without being dropped from the protocol.
- 4) The PI will review each participant carefully with study staff. Study participants who are judged by the PI to be in need of additional psychiatric or psychological evaluation/treatment or medical consultation will be referred as clinically indicated. This includes endorsement of self-harm and suicidality which will be addressed immediately. The participants will be frequently asked whether they desire additional referral or consultation for their own or their loved one's safety. If imminent danger is reported, participants will develop a safety plan with [name] as described below.
- 5) The PI will meet with staff staff and clinicians at least weekly for supervision. Staff will be trained to recognize signs of distress (for instance, hopeless statements) and will report to the PI both the content of interactions with participants as well as any concerns about their mood or concerning statements. If needed, study staff will provide crisis intervention, recommendations or referrals for adjunctive medical/pharmacological interventions, and when necessary, referral to emergency or inpatient treatment facilities. The PI will closely supervise or personally provide any crisis intervention. Staff will seek written release to coordinate care with other mental health providers prior to the start of treatment to avoid need for acute care when increased outpatient supports may be sufficiently garnered. Participants will be told they may decline to answer any questions or participate in any component. Staff will make the study assessments and MILO sessions as pleasant as possible by developing rapport and going at an appropriate pace so that participants do not become frustrated.
- 6) The PI does not believe this study poses significant risks to participants and does not anticipate any serious adverse events as a result of the study. However, first episode psychosis is associated with increased mortality in the community. Any safety concerns

relating to either the PCSO's or IP's wellbeing will be carefully discussed with the participant. Whenever reason for concern arises, the PI or other licensed clinician will evaluate safety risks and create a plan in collaboration with the participating PCSO to address such risk. This could involve calling 911 in cases of imminent safety threats. There is no reason to suspect that rates of illness complications will be higher if the parents or significant others of IP participate in the study.

- 7) Risks to subjects will be closely monitored as described in Section 6.1. Adverse events will be documented and reported per BMC/BUMC HRPP policies. Any event or set of events meeting the definition of Unanticipated Problem (UP) will be reported in an expedited timeframe (within 7 days) of the study team learning of the UP.
- 8) Staff will maintain regular contact with the IRB regarding study protocol, consents, recruitment materials, and human subject protection plan.

6.2 Potential Benefits

If it is effective, the intervention has tremendous upside to both participants and their loved ones with psychosis. The goals of the intervention are to shorten DUP, increase service utilization by the IP, and reduce caregiver distress. These parents and other loved ones are often desperate to seek help on behalf of the IP. Learning MI skills may benefit participants by reducing their stress, helping them to feel more confident in their caregiving role, and giving them information about how they can better facilitate the IP's connection or adherence to treatment.

Those randomized to the waitlist will be offered a 30-minute consultation during which the PCSO is provided with information about treatment options (e.g., community mental health and FEP coordinated specialty care programs) and contact information for an active NAMI chapter in his/her area. This will be done in person or by telephone. This consultation represents the minimum standard of care for caregivers of individuals with recent-onset psychosis being treated at BMC. Additionally, waitlist participants will have the opportunity to receive MILO training after a six-week wait.

Concerns about the ethics of randomization are allayed by the fact MILO is untested (effectiveness is not proven), and that waitlisted participants will also be offered the MILO intervention after a short waiting period.

6.3 Analysis of Risks in Relation to Benefits

This study will be of minimal risk to participants. There is a relatively low risk of harm to individuals receiving family therapies. Prior studies of family therapies with this and similar populations have demonstrated tolerability and efficacy. There are no physical risks of participating in this study and the study is not expected to be harmful or dangerous in any way. There are no manipulations of drug treatments. Pharmacotherapy is not required and if participants opt for it, they will be referred to appropriate providers. Thus the risk benefit ratio, even for those assigned to "waitlist", is favorable.

7 Study Subject Selection

7.1 Subject Inclusion Criteria

In order to be eligible to participate in this study, an individual must meet all of the following criteria:

- PCSO is 18 years or older
- PCSO is able to communicate in English
- PCSO is a primary care giver or an individual who has ≥20 hours weekly contact with an IP
- PCSO is able to provide informed consent by demonstrating that they understand the aims and structure of the study

Although the individual with psychosis will not participate in MILO, study staff will establish via the participating PCSO that the individual with psychosis is:

- Aged 15-35
- Has been diagnosed with a DSM-5 psychotic disorder by a health professional, OR has clearly observable (by the PCSO) symptoms/behaviors indicating psychosis
- Experienced onset of observed symptoms or first psychosis diagnosis occurred within past five years
- Is not optimally engaged in outpatient treatment

Identifiable information about the individual with psychosis is not kept in study records. The information gathered about the IP is based on participants' reporting and perceptions.

Subject Exclusion Criteria

An individual who meets any of the following criteria will be excluded from participation in this study:

- Current mental health crisis: if study staff determine that the potential participant is in serious emotional distress during the eligibility determination and consent process, staff will consult with the PI to determine whether the participant should be referred to psychiatric care to address their distress prior to participating in MILO

8 Study Intervention

The active intervention includes four to five 45-60 minute sessions. Sessions will be conducted individually with the clinician, or if two or more PCSO (e.g., parents) wish to participate together, they will meet at the same time with the clinician. The first two sessions will focus primarily on teaching through concept review, demonstration, and role play. In the third and fourth sessions, the clinician will learn about PCSOs' efforts to initiate a conversation about treatment with the IP using, and will provide feedback, problem-solving, and encouragement regarding the PCSO's

efforts. A fifth session may be offered upon request to provide additional coaching, consultation, and psychoeducation relevant to MILO topics. See Table 1 for details about session content.

Session	Content
1	Participants talk with a study clinician about the IP's illness history and how the experience has impacted them and their family. Treatment and psychoeducational resources are offered (e.g. NAMI support groups). Study staff teach participants about the philosophy of motivational interviewing and the potential value of listening and asking questions instead of giving advice or solving the problem.
2-3	Study staff teach participants core MILO communication skills (reflections, questions, asking permission before offering advice) and practice the skills during the session.
4-5 (5 th session optional depending on participants' preference)	Participants review their attempts to use MILO skills with the IP and receive feedback and encouragement from MILO clinicians. Participants have the opportunity to role play with the clinician to obtain additional practice.

The waitlist condition offers a one-time consultation session to participants while they are on a 6-week waitlist condition to receive MILO sessions. This involves a 30 minute consultation with a clinician experienced psychosis treatment with the goal of providing some psychoeducational resources. These resources include links to NAMI handouts, a directory of psychosis early intervention clinics, and information about psychiatric emergency services. This is similar to content addressed the first half of session 1 of MILO. Participants may decline this consultation and wait for the MILO intervention instead.

9 Study Procedures

See the Appendix for the schedule of events.

Event	Protocol
Contact	Potential participant contacts study staff via email or phone communication. This is a dedicated study phone number. Study staff schedule a 10 minute phone call with potential participant to review study details and complete pre-screen.
Pre-Screen	Study Staff confirm that potential participant is interested in learning more, reads the Consent to Phone Screen, asks eligibility criteria questions
Eligibility Determination	Study staff review the answers to the eligibility questions, if any answer is unknown or needs clinical input, study staff contacts the Principal

	Investigator. If contact is ineligible, they are told why and given other resources to consider.
Consent	If potential participant is eligible, they are offered a time to review the study consent with study staff. Once study details have been reviewed and study staff have made sure participants have no lasting questions, then study staff send the REDCap consent link to the participants. Participants are given study staff contact information if they have any more questions before signing the document via REDCap. If participants do not have access to necessary technology to complete a remote consent, they will be invited to [name] office. All in person operations will follow BMC's COVID procedures.
Baseline Assessments	Participants are sent a REDCap survey link after consent is complete via email and asked to schedule a 15 minute phone call with study staff to complete their baseline real play assessment
Randomization	Once baseline assessments are complete, study staff randomize participant into MILO or waitlist condition.
IF Waitlist Condition	Participants randomized to waitlist condition, are emailed the date that their waitlist period ends and offered a 30 minute treatment consultation with one of the MILO trainers before the 6 week waitlist period is complete. This treatment consultation can be completed over the phone, over a BMC Zoom, or in person at [name] office. All in person visits will follow BMC's COVID procedures. At the end of the waitlist period, they are sent REDCap surveys and asked to complete another real play assessment over the phone (first done at baseline).
MILO Treatment	Participants randomized to immediate MILO, as well as those who have already finished the waitlist period, are scheduled for their first MILO training session. Sessions are offered via a secure telehealth platform, HIPAA compliant Zoom or in person if the participant does not have access to appropriate technology. All in person operations will follow BMC's COVID procedures. Sessions are 45-60 minutes and participants are offered 4-5 sessions. All sessions are conducted by trained study staff. Study staff receive weekly individual supervision from the PI.

	Study staff utilize detailed guides to ensure high fidelity to the MILO intervention. Details of the intervention are described in the table above in section 8.
Post-Intervention Assessments	Once participants have completed MILO intervention, they are emailed their post-intervention REDCap survey and asked to schedule their last real play audio recorded exercise over the phone.
8 Week Follow Up	Participants are emailed a REDCap survey 8 weeks after their last MILO session.
12 Week Follow Up	Participants are emailed their last REDCap survey 12 weeks after their last MILO session.

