11.2 Sample Size Determination

The overall target for recruitment is 100 participants. 52 participants will be recruited for the protocol once approved by BMC (48 participants were recruited at Beth Israel Deaconess Medical Center which was the original recipient of the K23 funding support). This study is a pilot intended to test feasibility and preliminary effectiveness of the MILO intervention. Although true “pilot” studies focus an on intervention’s feasibility, rather than effects per se, the current study reflects a two-phase hybrid of priorities balancing the need to focus on feasibility while also investigating whether the intervention impacts the hypothesized treatment targets (MI skills, self-efficacy) and whether it is more effective in achieving the primary outcome (IP engagement in FEP treatment) than a control condition representing “treatment as usual” and a waiting period. The control group will be small relative to the active treatment group, thus maximizing the feasibility-focused sample. Thus the study may be somewhat underpowered to detect statistically significant effects, but has been designed to yield high quality feasibility metrics, highlight important factors for implementation, and provide a rough estimate of effect size that will inform a later, fully powered RCT.

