11.3 Statistical Methods

Feasibility will be analyzed using the following descriptive metrics: # participants screened; # Eligible; # Enrolled; # not enrolled and corresponding reasoning # Meeting DSM-5 Adjustment Disorder criteria; Percentage of Treatment sessions completed; Treatment Satisfaction; % assessments completed; Duration of assessments.

The outcomes of interest will be compared between the intervention and waitlist groups, and also within the waitlist group (comparing the pre-post intervention changes to the pre-post waitlist time changes. Prevalence of IP treatment seeking in each group will also be analyzed via odds ratios. Secondary outcomes, i.e. changes in PCSO distress and quality of life, will be

assessed via repeated measures ANOVAs examining group-by-time changes. Similarly, hypothesized mediators of effects (MI skill proficiency and self-efficacy) will be examined via repeated measures ANOVAs examining group-by-time changes. Analyses will be conducted using SPSS software.

12 Ethics/Protection of Human Subjects

This study is to be conducted according to applicable US federal regulations and institutional policies (which are based in federal regulations, guidance, and ICH Good Clinical Practice guidelines).

This protocol and any amendments will be submitted to the Boston Medical Center and Boston University Medical Campus IRB, for formal approval of the study conduct. The decision of the IRB concerning the conduct of the study will be made in writing to the investigator. A copy of the initial IRB approval letter will be provided to the sponsor before commencement of this study.

All subjects for this study will be provided a consent form describing this study and providing sufficient information for subjects to make an informed decision about their participation in this study. The consent form will be submitted with the protocol for review and approval by the IRB. The consent of a subject, using the IRB-approved consent form, must be obtained before that subject is submitted to any study procedure. Consent will be documented as required by the IRB.

13 Literature References

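### The entry criterion in 7.1 can admit IPs already in some outpatient care, and the 11.3 odds ratio on treatment seeking can count them as events from entry

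*Combined protocol and SAP*

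**What the plan says.** Section numbers follow the body of the document; the table of contents numbers the later sections differently.

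- **Section 3.2** presents MILO as an intervention for "parents or other concerned significant others (PCSO) of individuals with psychosis (IP) who refuse treatment". It adds: "The primary aim of the intervention is to increase the likelihood of IP engaging with evidence-based treatment".
- **Section 5** gives the study population as caregivers of "individuals experiencing psychosis (IP) who are not currently engaged with treatment".
- **Section 7.1**, the list applied at screening, asks only that the IP "Is not optimally engaged in outpatient treatment". It does not define optimal engagement, and the exclusion criteria do not remove IPs who are in care.
- **Section 11.3** states: "Prevalence of IP treatment seeking in each group will also be analyzed via odds ratios". It gives no definition of the event, no time point, no restriction to IPs untreated at entry and no baseline adjustment for this odds ratio.
- **Section 11.2** uses a narrower label for the outcome, asking "whether it is more effective in achieving the primary outcome (IP engagement in FEP treatment) than a control condition".
- **Section 4.2.2** schedules the "Past Month Service Use History" form at baseline and at every later assessment. Section 9 places randomisation after the baseline assessments.

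**The concern.** The three descriptions of the IP do not coincide, and the one used for screening is the widest. An IP who attends a clinic irregularly can satisfy 7.1 but does not fit section 5.

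This affects the analysis because 11.3 works with prevalence, not with new starts. For an IP already in outpatient care, treatment seeking may be present on the day of entry. What MILO could still change is how well that IP adheres or stays in care. If IPs already in care and IPs out of care are pooled in one prevalence, the between-arm contrast mixes two questions, and the estimate depends on an unreported case mix.

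The estimate matters even in a pilot. Sections 4.1 and 4.2 place engagement among the secondary aims, but 3.2 calls it the intervention's main aim and 11.2 calls it the primary outcome. Section 11.2 also says the trial should supply a rough effect size for a later full trial. An odds ratio diluted by an unknown amount is hard to carry forward for that purpose.

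**Working it through.** **The plan's own figure.** The only sample-size figure is the target of 100 in 11.2, and 48 + 52 = 100 checks. The plan gives no event rates, alpha, power or effect size, so all rates below are assumptions.

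**Inputs**
- New treatment starts among IPs untreated at entry: p = 0.20 (waitlist) and 0.40 (MILO), assumed.
- Share f already in outpatient care at entry, equal in both arms: assumed, 0 to 40%.
- In the base case, IPs already in care stay in it and count as events.
- 50 per arm, from 100 participants and the 50%/50% allocation in sections 2 and 5. Section 11.2 speaks of a small control group, so equal arms are also an assumption.

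**Odds ratio.** Observed prevalence = f + (1 − f) × p.

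| f | Waitlist | MILO | Odds ratio |
|---|---|---|---|
| 0 | 0.20 | 0.40 | (0.40/0.60)/(0.20/0.80) = 2.67 |
| 20% | 0.2 + 0.8 × 0.2 = 0.36 | 0.2 + 0.8 × 0.4 = 0.52 | (0.52/0.48)/(0.36/0.64) = 1.93 |
| 30% | 0.3 + 0.7 × 0.2 = 0.44 | 0.3 + 0.7 × 0.4 = 0.58 | (0.58/0.42)/(0.44/0.56) = 1.76 |
| 40% | 0.4 + 0.6 × 0.2 = 0.52 | 0.4 + 0.6 × 0.4 = 0.64 | (0.64/0.36)/(0.52/0.48) = 1.64 |

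**If MILO also improves retention.** Assume 30% of those already in care leave it on the waitlist and 15% leave it on MILO.
- f = 20%: waitlist 0.2 × 0.70 + 0.8 × 0.20 = 0.30; MILO 0.2 × 0.85 + 0.8 × 0.40 = 0.49; odds ratio (0.49/0.51)/(0.30/0.70) = 2.24.
- f = 40%: waitlist 0.4 × 0.70 + 0.6 × 0.20 = 0.40; MILO 0.4 × 0.85 + 0.6 × 0.40 = 0.58; odds ratio (0.58/0.42)/(0.40/0.60) = 2.07.

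**Power** (two-sided 0.05, normal approximation, d = difference, p̄ = mean rate):
power = Φ{[d − 1.96√(2p̄(1 − p̄)/n)] / √[(p₁(1 − p₁) + p₂(1 − p₂))/n]}.
- All participants, f = 0: 59%.
- All participants, f = 20%: Φ[(0.16 − 1.96 × 0.0993)/0.0980] = Φ(−0.35) = 36%. At f = 30%: 29%.
- Only IPs untreated at entry, f = 20%, n = 50 × 0.8 = 40 per arm: Φ[(0.20 − 1.96 × 0.1025)/0.1000] = 50%. At f = 30%, n = 35 per arm: 45%.

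In the base case the smaller, restricted comparison keeps the odds ratio at 2.67 and has more power than the pooled one.

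**Chance imbalance.** The SD of the between-arm difference in the share already in care is √(2f(1 − f)/50). It is √(2 × 0.2 × 0.8/50) = 0.08 at f = 20% and 0.09 at f = 30%. The observable differences are 0.16 and 0.14.

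**The case against.** The best defence is that the wider population is intended. The aims in 4.1 and the hypotheses in 11.1 are not limited to IPs who refuse care. Section 3.1 speaks of adherence as well as seeking care, 3.2 itself mentions under-treatment, and 6.2 covers adherence as well as connection to treatment. The 7.1 criterion fits all of these. This stands, and it means the repair may belong in the wording of 3.2 and 5 and not in 7.1. It does not tell the reader how an IP in care at entry is counted in 11.3.

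A second defence is that the odds ratio is not the only engagement analysis. Section 11.3 also compares outcomes of interest between groups and looks at pre-post changes within the waitlist group; 11.1 lists IP engagement among those outcomes and frames its third hypothesis as improvement. This also stands, but none of it is carried into the odds ratio.

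Four stronger readings are tempting and are not supported:
- *Some enrolled IPs were in care at entry.* No count is given. Whether such an IP would be an event also depends on a missing definition; under the narrower label in 11.2, general outpatient care might not qualify.
- *Anyone admitted by 7.1 but in partial care contradicts both other descriptions.* An IP who sees a therapist but declines medication could fairly be said to refuse treatment in the sense of 3.2.
- *The result will be biased towards one arm.* Randomisation balances entry status on average. The effect is dilution, plus possible chance imbalance.
- *An IP who starts care between the phone screen and baseline is wrongly randomised.* The documents give no interval, and starting care is not in itself disqualifying under 7.1.

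**Conclusion.** The point holds as a conditional one. Sections 3.2 and 5 do not match the operative criterion in 7.1. As written, the odds ratio in 11.3 can count IPs already in outpatient care as events from entry, although the form that would identify them is scheduled before randomisation.

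The size is unknown because the share in care at entry is not given. On assumed new-start rates of 20% and 40%, with those in care staying in it, the odds ratio falls from 2.67 to 1.93 at a 20% share and to 1.64 at 40%. With the assumed retention benefit it falls only to 2.24 and 2.07. Section 11.2 already concedes limited power, so the consequence is mainly for the interpretation of the effect estimate. The change should be made, and it leaves recruitment as it is.

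**What to change.** 1. Reconcile 3.2, 5 and 7.1 on which IPs are enrolled, and say what optimal engagement means at screening. If the wider group is intended, say so in 3.2 and 5.
2. In 4.2.2 and 11.3, define the engagement event (any outpatient care, or FEP treatment as in 11.2) and its time point.
3. Use baseline Past Month Service Use in the engagement analysis. Estimate new engagement among IPs with no outpatient treatment at baseline. For the full sample, adjust for or stratify on baseline status. Report IPs already in care separately, on change in service use.
4. Report baseline treatment status by arm.

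**Cost.** The plan's text changes, and no new assessment is scheduled. The new-engagement estimate uses fewer participants, for example 40 per arm in place of 50 at a 20% share. Two things need checking. The form's items are not shown, so it must be confirmed that they identify outpatient contact. It must also be confirmed that the form is available for the 48 participants recruited at the first site. A one-month window has a limit of its own: an irregular attender with no contact in that month would be classed as untreated, and a later visit would look like a new start. The Mental Health Service Use History, also scheduled at baseline, may help to separate these cases.
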